1.1.3 Clinical Experience with GLA-AF

Both *Na-GST-1/Alhydrogel*[®] and *Na-APR-1 (M74)/Alhydrogel*[®] are being tested in combination with the Toll-like Receptor 4 (TLR4) agonist, Gluco-Pyranosylphospho-Lipid A in Aqueous Formulation (GLA-AF, Infectious Diseases Research Institute [IDRI], Seattle, WA). GLA-AF contains a synthetic monophosphoryl lipid A (MPL) molecule that has TLR4 agonist activity. MPL is itself derived from the lipopolysaccharide (LPS) of *Salmonella minnesota*, a natural TLR4 agonist that is pyrogenic and can induce toxic shock. LPS, and more specifically, its lipid A component, has long been known for its strong adjuvant effects; however, its high toxicity has precluded its use in a vaccine formulation. Ribi et al showed that the monophosphorylated form of lipid A retains its adjuvant function and almost completely loses its endotoxin effects (40).

There have been many clinical trials involving thousands of subjects in which MPL or a derivative have been administered as vaccine adjuvants to adults and children, including vaccines for human papillomavirus, malaria (41-43), leishmaniasis (44), and hepatitis B (45). In general, these trials have demonstrated that administering MPL to humans is safe and well tolerated; when compared to formulations of vaccine that do not contain MPL, those adjuvanted with MPL may result in a minor increase in the incidence and/or severity of local injection site reactions. However, the addition of MPL also often results in a much improved specific antibody response to the vaccine antigen(s).

Of note, MPL is one of the components of the licensed Cervarix[®] vaccine (GlaxoSmithKline, Research Triangle Park, NC) for the prevention of cervical cancer due to human papillomavirus serotypes 16 and 18. The adjuvant for this vaccine consists of MPL adsorbed to aluminum hydroxide salt and is therefore similar to the combination of GLA-AF and Alhydrogel[®] that we propose testing in combination with *Na-GST-1* and *Na-APR-1 (M74)* in the study described in this protocol. The Cervarix[®] vaccine has been shown to have a very favorable safety profile after having been tested in tens of thousands of healthy individuals (46, 47).

As mentioned previously, up to 5 µg of GLA-AF has been administered to a small number of human volunteers in combination with both *Na-GST-1/Alhydrogel*[®] and *Na-APR-1 (M74)/Alhydrogel*[®]. In addition, an oil-in-water emulsion of GLA (GLA-SE) has been used in combination with the Fluzone[®] trivalent killed influenza vaccine in a Phase 1 trial. In this study, doses up to 2.5 µg of GLA-SE were safe and well-tolerated and significantly enhanced influenza-specific antibody responses (48).

1.2 Rationale

1.2.1 Rationale for the Study

A product that combines *Na-GST-1* and *Na-APR-1* (M74) shows promise as an effective bivalent hookworm vaccine because vaccination of laboratory animals with recombinant *Na-GST-1* or *Na-APR-1* results in significant protection from challenge infections (29, 37). Therefore, vaccination of humans with recombinant *Na-GST-1* or *Na-APR-1* (M74) holds promise for inducing protection against this infection, particularly the moderate and heavy intensity infections that are associated with clinical sequelae such as intestinal blood loss and iron-deficiency anemia. The Sabin Vaccine Institute has sponsored a series of Phase 1 trials of the *Na-GST-1* and *Na-APR-1* (M74) candidate antigens in healthy adult volunteers from hookworm endemic areas (Brazil) and non-endemic areas (USA). Given the results of preclinical testing in laboratory animals, it is thought that a vaccine based on a single antigen will not be sufficient to provide adequate protection from disease (49). Instead, the goal is to develop a multi-component vaccine containing at least two recombinant proteins targeting different steps in the hookworm digestion of host hemoglobin. As such, a necessary step in clinical development is to test whether combining *Na-GST-1* and *Na-APR-1* (M74) results in an increased safety risk or reduced immunogenicity to either antigen, compared to when they are administered individually.

As a necessary first step, *Na-GST-1* and *Na-APR-1* (M74) were co-administered to healthy adults in Gabon, as described above in Section 1.1.1. However, given that the main target for an eventual vaccine will be children living in hookworm-endemic areas, pediatric Phase 1 trials are required to evaluate safety and immunogenicity in the target population prior to conducting larger-scale Phase 2 and 3 clinical trials.

1.2.2 Rationale for Doses and Dose Schedule to be Studied

Na-APR-1 (M74)/Alhydrogel® and *Na-GST-1*/Alhydrogel® (with or without GLA-AF) have been tested at the same field site as that proposed in the study described in this protocol, in healthy hookworm-exposed adults without any observed safety concerns. Therefore, in the study described in this protocol, these two vaccine products will be administered in escalating doses, to school-age children who live in an area where hookworm is endemic. Doses of 10, 30 and 100 µg of *Na-APR-1* (M74) and *Na-GST-1*/Alhydrogel® were selected for evaluation based on preclinical studies and to maintain an equal fold-increase in the amount of antigen. The 10 µg dose was also selected as the lowest dose for clinical trials due to the difficulty in precisely dispensing lower volumes (both vaccine antigens have been formulated at a protein concentration of 100µg/ml). Selection of the maximum 100 µg doses of *Na-GST-1* and *Na-APR-1* (M74) is based on the safety and immunogenicity data from the Phase 1 studies of these antigens that have been conducted in adults, in which this was the maximum dose tested.

To date, up to 100 µg *Na-APR-1* (M74)/Alhydrogel® administered with 5 µg GLA-AF has been very well tolerated in healthy adults, with no observed vaccine-related Serious Adverse Events and only mild to moderate local injection site pain and tenderness being the most commonly reported adverse events. However, the addition of GLA-AF to *Na-GST-1*/Alhydrogel did not significantly increase IgG levels to the *Na-GST-1* antigen. Therefore, GLA-AF will not be tested further in combination with *Na-GST-1*/Alhydrogel.

For the study proposed in this clinical protocol, each child will be vaccinated three times, on Days 0, 56, and 112 or 180. On each vaccination day each child will receive two injections, one injection per arm. This vaccination schedule was selected to coordinate with the Expanded Program on Immunization as the human hookworm vaccine is intended to target children, including eventually infants. Two different vaccination schedules are being tested (i.e., 0, 2, 4 months vs. 0, 2, 6 months) to determine the optimal immunogenicity.

Local subcutaneous nodules, believed to be granulomatous reactions to aluminum hydroxide, have been observed with use of aluminum hydroxide-based adjuvants. Thus, most aluminum hydroxide-adsorbed vaccines are injected intramuscularly (IM) rather than subcutaneously, and intramuscular injection in the deltoid muscle will be used for administration of all investigational products in the study.

1.2.3 Clinical Development Plan for the Human Hookworm Vaccine

The target population for the human hookworm vaccine is children 10 years of age or younger living in hookworm endemic areas, since this is the age group that is most at risk of disease from this infection. Prior to conducting clinical trials in this age group, however, both *Na-GST-1* and *Na-APR-1* (M74) are currently being tested in healthy adults living in areas of high hookworm prevalence. Since co-administration of the two antigens in adults has not resulted in any significant safety concerns, testing is proceeding to Phase 1 testing in children living in hookworm endemic areas of Africa (Gabon, as described in this protocol) and Brazil. After safety and immunogenicity of the co-administered products is shown in children, testing of a co-formulated product that contains both *Na-GST-1* and *Na-APR-1* (M74) will be started, first in adults and then in children. The dose concentrations and components of the co-formulated product will be determined through the cumulative results of the study described in this protocol and the previous Phase 1 trials of these vaccine antigens.

The series of Phase 1 trials in adults and children described above will culminate in a large Phase 2 trial in which the co-formulated antigens will be administered to children living in endemic areas. The hookworm vaccine will be compared to a licensed comparator vaccine to evaluate the impact of mean fecal egg counts as well as a variety of clinical and parasitological endpoints. Assuming that an impact on infection is shown in the Phase 2 trial, that there are no new safety issues that arise due to co-formulation of the antigens, and that combining them into one product does not adversely affect the immunogenicity of either, this product will be tested in a pivotal multi-center Phase 3 trial in children. The primary endpoint of the Phase 3 trial will be the incidence of moderate and heavy hookworm infection (as determined by fecal egg counts) following administration of an anthelmintic and vaccination.

1.3 Potential Risks and Benefits

1.3.1 Potential Risks

Risks to subjects are those associated with venipuncture, intramuscular injection of the vaccines, possible reactions to the vaccines, and breach of confidentiality. Risks occasionally associated

with venipuncture include pain and bruising at the site of venipuncture, lightheadedness, and syncope (rarely). Intramuscular (IM) injection also may cause transient discomfort and fainting.

Possible local vaccine reactions include pain, swelling, erythema, induration, transient limitation of limb movement, lymphadenopathy, or pruritus at the injection site. Local subcutaneous nodules, believed to be granulomatous reactions to aluminum hydroxide, have been observed with use of aluminum hydroxide-based adjuvants, although these have not been observed with either *Na-APR-1* (M74)/Alhydrogel® or *Na-GST-1*/Alhydrogel® in the currently ongoing trials of these products. Regardless, most aluminum hydroxide-adsorbed vaccines are injected intramuscularly rather than subcutaneously. Systemic reactions such as fever, headache, malaise, myalgia, and joint pain, may also possibly occur. Immediate hypersensitivity reactions including urticaria, anaphylaxis, or other IgE-mediated responses are possible as with any vaccine. As with any investigational vaccine, there is a theoretical possibility of risks about which we have no present knowledge. Subjects will be informed of any such risks should further data become available.

Phase 1 trials of *Na-APR-1* (M74)/Alhydrogel® plus GLA-AF have demonstrated similar reactogenicity and safety to the antigen administered without GLA-AF. However, in a study of an influenza vaccine administered with GLA-SE (a formulation similar to GLA-AF), the frequency and intensity of local reactions were greater than when the vaccine was administered without GLA-SE (50).

1.3.2 Precautions Taken to Minimize Risks

In order to minimize the risk to subjects, all children will be monitored closely during their participation in this study. The study vaccines and GLA-AF have been produced according to current Good Manufacturing Practices (GMP) and will be administered by experienced investigators with drugs and equipment available for the treatment of anaphylaxis and other potential adverse reactions. All vaccine doses will be given by intramuscular injection to minimize injection site reactions such as pain.

Maintenance of Confidentiality

Participants will be asked to provide personal health information. All attempts will be made to keep this information confidential within the limits of the law. However, there remains the unlikely risk that unauthorized persons will see the subjects' personal health information. All records will be kept in a locked file cabinet or maintained in a locked room at the study site. Electronic files will be password protected. Only people who are involved in the conduct, oversight, monitoring, or auditing of this study will be allowed access to the personal health information that is collected. Any publications from this study will not use information that will identify subjects by name.

1.3.3 Known Potential Benefits

Children who are enrolled in the study may not receive any direct benefit from participation. It is hoped that information gained in this study will contribute to the development of a safe and effective hookworm vaccine. All children will undergo a stool examination for ova and parasites at screening and on Day 140 and Day 380 study visits. Those found to have a helminth infection

at either of these study visits will be offered appropriate treatment at the conclusion of the study, free-of-charge. Free medical treatment will be provided to all vaccinated subjects during the active immunization phase and the follow-up period. If the investigators judge that a subject requires hospitalization, transportation will be arranged and the medical management of the subject will be monitored by a study physician and the local Independent Safety Monitor. Medical care for ailments not related to vaccination will not extend beyond the study period, but will be referred to the nearest government-run health clinic. Medical care for ailments related to vaccination will extend at least until the condition has resolved or stabilized (if a chronic condition).

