2.2.3 Tertiary Outcome Measures

Immunogenicity

The following parameters will be evaluated for each dose of *Na-APR-1* (M74) co-administered with *Na-GST-1*:

1. The IgG antibody response as measured by a qualified indirect ELISA at approximately 7, 14, and 28 days after each vaccination, and approximately 3 and 6 months after the third dose.
2. The IgG subclass levels (IgG1, IgG3, and IgG4) against the vaccine antigens by indirect ELISA approximately 14 days after the third vaccination.

3. The IgG1-4 subclass levels as measured by indirect ELISA on each day of vaccination, approximately 28 days later, and approximately 3 and 6 months after the final vaccination.

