2.2.4 Exploratory Outcome Measures

The following parameters will be evaluated for each dose of *Na-APR-1* (M74) co-administered with *Na-GST-1*:

1. Cellular immune response will be measured by a qualified indirect ELISA at approximately on days of vaccination, and then 7, 14, and 28 days after each vaccination, and approximately 3 and 6 months after the third dose.
2. Metabolomic profiles before vaccination, on days of vaccination, approximately 7 and 28 days following each vaccination, and 6 months after the third dose.

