6.1 Screening

The following procedures will be performed upon initial screening (note that all procedures might not be performed on the same day):

1. Explain the study, Informed Consent and the child assent form to the child's parent/legal guardian.
2. Ensure the child's parent/legal guardian has passed the informed consent comprehension questionnaire, has signed the Informed Consent as well as the child assent form and receives a signed copy of the Informed Consent.
3. Elicit a complete medical history, including medication history, for the child.
4. Administer a physical examination, including vital signs (heart rate, respiratory rate, arterial blood pressure, and a tympanic temperature).
5. Obtain blood for hematology, biochemistry, and serologic tests for HIV and viral hepatitis (B and C).
6. Obtain fecal sample for examination for ova and parasites.
7. Obtain urine for urine dipstick testing and examination for ova.
8. Obtain urine for metabolomics study.

Screening steps 3-7 must be performed within 90 days before the planned enrollment into the study. Should this screening window be exceeded before the first vaccination, screening procedures (not including administration of the informed consent form or comprehension questionnaire) may be repeated to ensure continued eligibility for the study (screening procedures can be repeated a maximum of one time). Screening laboratory tests (other than serologic tests for HIV and viral hepatitis) may be repeated up to one time to confirm any abnormalities.

If the fecal exam performed during screening demonstrates infection with an intestinal parasite the child will be treated with an appropriate medication prior to being enrolled in the study and before any vaccinations. Children infected with *Ascaris lumbricoides*, hookworm or *Trichuris trichiura* will be treated with three daily 400 mg doses of albendazole; children infected with *S. intercalatum* or *Taenia* spp. will be treated with a single 40 mg/kg oral dose of praziquantel; and individuals infected with *Strongyloides stercoralis* will be treated with three 400 mg daily oral doses of albendazole. If the urine exam performed during screening demonstrates infection with *Schistosoma haematobium*, infected children will be treated with a single 40 mg/kg oral dose of praziquantel. Children who have been treated for any parasitic infections, cannot be enrolled for vaccination within 14 days after the last day of treatment.

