1. Perform basic history and physical exam (including injection site), emphasizing examination of any acute complaints.
2. Record vital signs.
3. Obtain blood for hematology, biochemistry, anti-Na-GST-1 and anti-Na-APR-1 (M74) humoral and cellular immunology assays.
4. Obtain a urine sample for metabolomics study.

Study Day 140 (28 +/-4 days after Third Vaccination) [Groups 1a, 2a, & 3a ONLY]

1. Perform basic history and physical exam, emphasizing examination of any acute complaints.
2. Obtain blood for anti-Na-GST-1 and anti-Na-APR-1 (M74) antibody assays and cellular immunology assays.
3. Obtain stool for examination for ova and larvae from parasites.
4. Obtain a urine sample for metabolomics study.

Study Day 200 (3 months +/-14 days after Third Vaccination) [Groups 1a, 2a, & 3a ONLY]

1. Perform basic history and physical exam, emphasizing examination of any acute complaints.
2. Obtain blood for anti-Na-GST-1 and anti-Na-APR-1 (M74) humoral and cellular immunology assays.
3. Obtain a urine sample for metabolomics study.

Study Day 208 (28 +/-4 days after Third Vaccination) [Groups 1b, 2b, & 3b ONLY]

1. Perform basic history and physical exam, emphasizing examination of any acute complaints.
2. Obtain blood for anti-Na-GST-1 and anti-Na-APR-1 (M74) humoral and cellular immunology assays.
3. Obtain stool for examination for ova and larvae from parasites.
4. Obtain a urine sample for metabolomics study.

Study Day 268 (3 months +/-14 days after Third Vaccination) [Groups 1b, 2b, & 3b ONLY]

1. Perform basic history and physical exam, emphasizing examination of any acute complaints.
2. Obtain blood for anti-Na-GST-1 and anti-Na-APR-1 (M74) humoral and cellular immunology assays.
3. Obtain a urine sample for metabolomics study.

Study Day 290/358 (6 months +/-14 days after Third Vaccination)

1. Perform basic history and physical exam, emphasizing examination of any acute complaints.
2. Obtain blood for anti-Na-GST-1 and anti-Na-APR-1 (M74) humoral and cellular immunology assays.
3. Obtain a urine sample for metabolomics study.

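### Section 1.3.3 defers the treatment offer for a helminth infection found at the Day 140/208 stool test to study end, about 240 days later, without a reason; sample protection could justify at most about the first 150 days.

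*Combined protocol and SAP*

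**What the plan says.** Section 1.3.3 names stool examinations at screening, Day 140 and Day 380. Children positive at a study visit "at either of these study visits will be offered appropriate treatment at the conclusion of the study, free-of-charge". The next sentence reads "Free medical treatment will be provided to all vaccinated subjects during the active immunization phase and the follow-up period". Nothing says how the two relate, and no reason for the deferral appears anywhere in the document.

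An infection found at screening is handled differently. Under Section 6.1 "the child will be treated with an appropriate medication prior to being enrolled in the study and before any vaccinations". For hookworm, *Ascaris* and *Trichuris*, infected children "will be treated with three daily 400 mg doses of albendazole".

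Section 6.3 schedules the post-vaccination stool test ("Obtain stool for examination for ova and larvae from parasites") at Day 140 for the 0,2,4-month groups. For the others it falls at "Study Day 208 (28 +/-4 days after Third Vaccination) [Groups 1b, 2b, & 3b ONLY"]. Section 6.4 sets the final visit at Day 380/448, with history, examination and stool only.

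No outcome in Section 2.2 uses a stool result. The IgG outcome in Section 2.2.3 is measured "at approximately 7, 14, and 28 days after each vaccination, and approximately 3 and 6 months after the third dose". In Section 2.2.4 the cellular outcome also ends at 6 months after the third dose, and the metabolomic outcome is "Metabolomic profiles before vaccination, on days of vaccination, approximately 7 and 28 days following each vaccination, and 6 months after the third dose".

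**The concern.** Followed literally, the specific rule means that a child aged 6 to 10 with a known infection is not offered treatment for about eight months, for no stated purpose. Section 1.1.1 (the hookworm background) links chronic hookworm infection and the resulting anemia to impaired development in children. The last scheduled blood count is at Day 126/194, before the stool result exists, so no hemoglobin is scheduled during the wait.

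There is a smaller data issue. If a clinician treats earlier under the general promise of care, the record may not show it. Section 5.5 opens by saying that any medication is recorded. It then defines the period as up to 28 days after each dose, and after that only for new-onset chronic conditions. Section 6.6 reviews drugs started within 28 days of a vaccination. The stool test itself falls 24 to 32 days after dose 3, so treatment that follows the result would usually start at or beyond that limit. Without drug and date on file, the 3- and 6-month tertiary and exploratory analyses could not take the exposure into account.

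**Working it through.** Inputs: third vaccination on Day 112 or 180; stool test on Day 140 or 208 (±4); 3-month visit on Day 200 or 268 (±14); 6-month visit on Day 290 or 358 (±14) (all Section 6.3); final visit on Day 380 or 448 (±21) (Section 6.4); last blood count on Day 126 or 194 (±2) (Section 6.3).

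The plan's own figure first. The final visit is described as 9 months after dose 3: 380 − 112 = 448 − 180 = 268 days, about 8.8 months. This agrees within the ±21-day window.

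The intervals are identical on the two schedules. Windows are shown for the 0,2,4-month groups.

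| Interval | Nominal days | Shortest | Longest |
|---|---|---|---|
| Stool test to final visit | 380 − 140 = 448 − 208 = 240 | 359 − 144 = 215 | 401 − 136 = 265 |
| Stool test to 6-month samples | 290 − 140 = 358 − 208 = 150 | 276 − 144 = 132 | 304 − 136 = 168 |
| 6-month samples to final visit | 380 − 290 = 448 − 358 = 90 | 359 − 304 = 55 | 401 − 276 = 125 |
| Stool test to next visit | 200 − 140 = 268 − 208 = 60 | 186 − 144 = 42 | 214 − 136 = 78 |
| Last blood count to final visit | 380 − 126 = 448 − 194 = 254 | 359 − 128 = 231 | 401 − 124 = 277 |

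What the wait could protect:

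- Days 140/208 to 290/358: antibody, cellular and urine samples are taken at 3 and 6 months. Section 7.2.2.5 plans urine sampling to measure metabolite change after anthelmintic drugs, so avoiding drug exposure before these samples is a plausible, though unstated, reason.
- Days 290/358 to 380/448: Section 6.4 schedules no blood or urine. The Appendix A1 cumulative blood volume stays at 94 mL from Day 290 to Day 380, which matches the study total of about 94 mL in Section 6. Only the final stool result could be changed by earlier treatment, and it feeds no listed outcome.

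Two entries point the other way. Section 10.2.2 adds antibody responses at Day 380/448 to the final analysis, with no matching blood draw in Section 6.4. The Appendix A2 urine row, as extracted, may carry a mark at Day 448. That table is misaligned in extraction (its total-volume row has 23 entries for 22 columns), so nothing is rested on it.

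**The case against.** A reader might infer that the plan obliges staff to leave an infected child untreated for eight months. The documents do not go that far. Section 1.3.3 is a benefits summary, and its next sentence promises free care during follow-up. Section 5.5 does not name anthelmintics among the drugs to avoid. Section 8.2.4 requires abnormal clinical findings to be followed appropriately. Clinicians are available throughout, visits continue at 3, 6 and 9 months, and Section 7.2.1 allows a repeat blood count if an adverse event indicates one. What stands is that the only sentence specific to helminths sets a late date, and staff cannot tell which sentence governs.

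A reader might also infer that treatment on the day of the result is plainly right. It is a trade-off: it places anthelmintic exposure before the 3- and 6-month samples, and Section 7.2.2.5 treats such drugs as a source of metabolite change. That reason reaches only to Day 290/358.

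A third inference would be that every immunological measurement certainly ends at Day 290/358. That holds for Section 2.2 and the visit lists, but Section 10.2.2 conflicts with it. If a Day 380/448 blood draw is intended, the last 90 days would have a possible purpose, and the protocol would need to say so.

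Finally, harm is not quantified. Hookworm found at screening is treated, hemoglobin below 9.5 g/dl excludes a child (Section 4.2), and Section 1.1.1 ties hookworm disease mainly to moderate and heavy infection. This limits the weight of the point but does not supply a reason for the delay.

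**Conclusion.** The point holds as a cheap improvement to child safety and clarity, not as a threat to the main results. The treatment offer is deferred by about 240 days (215 to 265) with no stated reason. About 150 days (132 to 168) could be explained by protecting samples. The remaining 90 (55 to 125) have no purpose in the Section 2.2 outcomes or in the visit schedule, subject to reconciling Section 10.2.2. The primary safety outcomes and the secondary IgG outcome, measured about 14 days after dose 3, are unaffected. The recording gap matters only for tertiary and exploratory samples taken after an early treatment.

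Assumptions: the conclusion of the study means the child's own final visit. If it meant the end of the whole trial, an early child on the 0,2,4-month schedule could wait 448 − 140 = 308 days, or 398 with an assumed 90-day enrollment span. The documents give no expected Kato-Katz positivity or infection intensity at the Day 140/208 test, so the number of children affected is unknown. Consent pages were not available, so disclosure to parents is not judged.

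**What to change.** 1. Section 1.3.3: offer a child positive at Day 140/208 the Section 6.1 regimen for that parasite, free of charge and alike in both arms, no later than directly after the Day 290/358 samples. State sample protection as the reason for any wait until then. Say that earlier treatment is allowed when clinically indicated.
2. Section 1.3.3: name the post-vaccination stool days as Day 140/208 and Day 380/448. This is wording only; Sections 6.3 and 6.4 already schedule the tests.
3. Sections 5.5 and 6.6: record drug, dose and date of any antiparasitic treatment through Day 380/448. Flag samples taken after such treatment in the tertiary and exploratory analyses.
4. Sections 10.2.2 and 6.4: either drop the Day 380/448 antibody point or schedule the blood draw.

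Treating as soon as the result is known would remove nearly all of the 240 days. The sponsor can weigh this against drug exposure before the 3- and 6-month samples. It would also need an off-schedule contact, because the next visit is 60 days (42 to 78) away and the hookworm regimen takes three days.

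Cost: a text amendment, one CRF line, and matching consent wording if the form repeats the rule. Free treatment is already promised, so it mainly moves forward. The final stool result may change, and a child re-infected by Day 380/448 may need a second course. The Day 290/358 limit still leaves a wait of about 150 days for a child with no clinical indication, which is why its reason should be written down.
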